5.2. Pharmacodynamic Analysis Set

None.

5.3. Safety Analysis Set

All participants assigned to study intervention and who take at least 1 dose of study intervention. Participants will be analyzed according to the product they actually received.

5.4. Other Analysis Sets

None.

5.5. Treatment Misallocations

This is a nonrandomized study. All subjects will receive the same treatment.

5.6. Protocol Deviations

Subjects who experience events that may affect their PK profile (eg, lack of compliance with dosing) may be excluded from the PK analysis. At the discretion of the pharmacokineticist a concentration value may also be excluded if the deviation in sampling time is of sufficient concern or if the concentration is anomalous for any other reason.

A full list of protocol deviations will be compiled and reviewed to identify major and minor deviations prior to database closure.

5.6.1. Deviations Assessed Prior to Randomization

At Screening, the investigator will assess subjects against the inclusion and exclusion criteria as set out in Sections 5.1 and 5.2 of the protocol.

5.6.2. Deviations Assessed Post-Randomization

A full list of protocol deviations for the study report will be compiled prior to database closure. Any significant deviation from the protocol will be reviewed prior to database closure and a decision taken regarding evaluation for each analysis population.

6. ENDPOINTS AND COVARIATES

6.1. Efficacy Endpoint(s)

None.

6.2. Safety Endpoints

An adverse event will be considered a Treatment-emergent Adverse Event (TEAE) if the event started during the effective duration of treatment. All events that starts on or after the first dosing day and time/start time, if collected, but before the last dose plus the lag time (28 days) will be flagged as TEAEs. The algorithm will not consider any event that started prior to the first dose date. Any event occurring following start of treatment or increasing in severity will be counted as treatment emergent.

The following data are considered in standard safety summaries (see protocol for collection days and list of parameters):

- *adverse events,*
- *laboratory data,*
- *vital signs data,*
- *ECG results.*

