1.3. Schedule of Activities

The SoA table provides an overview of the protocol visits and procedures. Refer to the **STUDY ASSESSMENTS AND PROCEDURES** section of the protocol for detailed information on each procedure and assessment required for compliance with the protocol.

The investigator may schedule visits (unplanned visits) in addition to those listed in the SoA table, in order to conduct evaluations or assessments required to protect the well-being of the participant.

Visit Identifier Abbreviations used in this table may be found in 10.9.	Screening	Period 1							Follow-Up	Early Termination/ Discontinuation
Days Relative to Day 1	Day -28 to Day -2	Day -1	Day 1	Day 2	Day 3	Day 4	Day 5	Day 6-14	28-35 Days ^b	
Informed consent	X									
CRU confinement ^a		X	X	X	X	X	X	X ^a		
Inclusion/exclusion criteria	X	X								
Medical/medication history	X	X								
Physical exam ^b		X						X ^c		X
Safety laboratory ⁱ	X	X						X ^c		X
Demography	X									
Height and Weight	X									
Urine drug/alcohol/cotinine testing ^k	X	X								
12-Lead ECG	X		X ^{g,j}					X ^c		X
Blood pressure and pulse rate	X		X ^{h,j}					X ^c		X
Contraception check									X	
HIV, HBsAg, HCVAb	X									
COVID-19 CRU Internal Procedure ^d	X	X	X	X	X	X	X	X ^c		X
Study intervention administration			X							
Standard Meals ^e		X	X	X	X	X	X			
Spot Collection for Urinalysis (and Microscopy, if needed)	X	X						X ^c		X
Retained Research Sample for Genetics (Prep D1) ^f			X							
CRU discharge								X ^a		
Serious and nonserious AE monitoring	X	X	X	X	X	X	X	X	X	X

PFIZER CONFIDENTIAL

Visit Identifier Abbreviations used in this table may be found in 10.9 .	Screening	Period 1						Follow-Up	Early Termination/ Discontinuation	
Days Relative to Day 1	Day -28 to Day -2	Day -1	Day 1	Day 2	Day 3	Day 4	Day 5	Day 6-14	28-35 Days ^b	

- a. Inpatient stay must be extended until >90% radioactive dose administered has been recovered or <1% is excreted in total (urine and feces) in any 24H period for two consecutive days. Maximum confinement will be 14 days.
- b. Complete physical examination will be conducted at Day -1 (Period 1); otherwise brief physical exam envisioned for findings during previous PE or new/open AEs, at Investigator discretion. Follow-up over the phone may be conducted if no new/open AE's at Investigators discretion.

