8.3.1. Time Period and Frequency for Collecting AE and SAE Information

The time period for actively eliciting and collecting AEs and SAEs (“active collection period”) for each participant begins from the time the participant provides informed consent, which is obtained before the participant’s participation in the study (ie, before undergoing any study-related procedure and/or receiving study intervention), through and including a minimum of 28 calendar days, except as indicated below, after the last administration of the study intervention.

Follow-up by the investigator continues throughout and after the active collection period and until the AE or SAE or its sequelae resolve or stabilize at a level acceptable to the investigator.

For participants who are screen failures, the active collection period ends when screen failure status is determined.

If the participant withdraws from the study and also withdraws consent for the collection of future information, the active collection period ends when consent is withdrawn.

If a participant permanently discontinues or temporarily discontinues study because of an AE or SAE, the AE or SAE must be recorded on the CRF and the SAE reported using the CT SAE Report Form.

Investigators are not obligated to actively seek information on AEs or SAEs after the participant has concluded study participation. However, if the investigator learns of any SAE, including a death, at any time after a participant has completed the study, and he/she considers the event to be reasonably related to the study intervention, the investigator must promptly report the SAE to Pfizer using the CT SAE Report Form.

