10.1.7. Data Quality Assurance

All participant data relating to the study will be recorded on printed or electronic CRF unless transmitted to the sponsor or designee electronically (eg, laboratory data). The investigator is responsible for verifying that data entries are accurate and correct by physically or electronically signing the CRF.

Guidance on completion of CRFs will be provided in the CRF Completion Requirements document.

The investigator must ensure that the CRFs are securely stored at the study site in encrypted electronic and/or paper form and are password-protected or secured in a locked room to prevent access by unauthorized third parties.

QTLs are predefined parameters that are monitored during the study. Important deviations from the QTLs and any remedial actions taken will be summarized in the clinical study report.

The investigator must permit study-related monitoring, audits, IRB/EC review, and regulatory agency inspections and provide direct access to source data documents. This verification may also occur after study completion. It is important that the investigator(s) and their relevant personnel are available during the monitoring visits and possible audits or inspections and that sufficient time is devoted to the process.

Monitoring details describing strategy, including definition of study critical data items and processes (eg, risk-based initiatives in operations and quality, such as risk management and mitigation strategies and analytical risk-based monitoring), methods, responsibilities, and requirements, including handling of noncompliance issues and monitoring techniques (central, virtual, or on-site monitoring), are provided in the data management plan and monitoring plan maintained and utilized by the sponsor or designee.

The sponsor or designee is responsible for the data management of this study, including quality checking of the data.

Records and documents, including signed ICDs, pertaining to the conduct of this study must be retained by the investigator for 15 years after study completion unless local regulations or institutional policies require a longer retention period. No records may be destroyed during the retention period without the written approval of the sponsor. No records may be transferred to another location or party without written notification to the sponsor. The investigator must ensure that the records continue to be stored securely for as long as they are maintained.

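### SAP 6.2 both bars and counts as treatment emergent an AE that starts before the first dose date and worsens after dosing under the same record

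*SAP*

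**What the plan says.** The TEAE rule is in the first paragraph of SAP 6.2 (Safety Endpoints). Its four sentences do the following.

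1. An AE is treatment emergent "if the event started during the effective duration of treatment".
2. Events are flagged when they start at or after dosing (using the time of day where it was collected) "but before the last dose plus the lag time (28 days) will be flagged as TEAEs".
3. "The algorithm will not consider any event that started prior to the first dose date".
4. "Any event occurring following start of treatment or increasing in severity will be counted as treatment emergent".

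Protocol 8.3.1 says that the active collection period "begins from the time the participant provides informed consent". The Schedule of Activities (Protocol 1.3) marks the row "Serious and nonserious AE monitoring" at Screening and at Day -1, as well as after dosing. SAP 8.3.4 gives no further TEAE rule and refers to the sponsor's reporting standards. Safety and tolerability is a secondary objective (SAP 2.2.2).

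**The concern.** The third sentence is absolute: onset before the dose date takes the event out. The fourth joins two routes to TEAE status with 'or', and the second route is worsening. The first route already covers everything that occurs after treatment starts. The worsening route therefore adds something only for events whose onset came before dosing, and nearly all of those are the events that the third sentence removes.

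Two programmers who each follow the text could give the same record opposite flags. The record at stake is one for which a treatment-emergent flag is informative: a complaint that was present before the dose and became worse after it. Followed literally, the third sentence keeps that worsening out of the TEAEs.

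**Working it through.** The plan gives no figure to reproduce, so the check is to apply each sentence to the possible kinds of record. I take worsening to mean a higher severity after dosing than before it. SAP 6.2 gives no reference point, and this is the natural reading.

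| Record | Sentences 1 and 2 | Sentence 3 | Sentence 4 | Result |
|---|---|---|---|---|
| (a) Onset after dosing, within the window | Counted | Not affected | Counted | Consistent |
| (b) Onset before the dose date, no worsening | Not captured | Barred | Not counted | Consistent |
| (c) Onset before the dose date, worse after dosing, same record | Not captured | Barred | Counted | **Conflict** |
| (d) Onset on the dosing date but before the dose (time collected), worse after dosing | Not captured | Not barred, since it works on the date | Counted | Counted only through sentence 4 |

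*Can case (c) occur?* Yes. Collection starts at consent, Screening can begin at Day -28, and AE monitoring is marked at Screening and Day -1. An AE with onset before Day 1 can therefore be in the database. The documents give no rate for such events or for their worsening.

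*Does another section settle it?*

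- Protocol 10.3.1 makes an exacerbation of a preexisting condition an AE. It does not say whether an AE already on the CRF gets a new record and onset date when it worsens.
- Protocol 10.3.3 has each AE assigned to one intensity category, which hints at a new record. The same section has new or updated information entered in the documents already submitted, which hints at the same record.
- SAP 8.3.4 defers to sponsor standards that are not reproduced.
- Protocol 10.1.7 says "Guidance on completion of CRFs will be provided in the CRF Completion Requirements document". That document might settle the matter, but it is not part of the protocol or SAP.

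*Size.* The inputs are 6 participants dosed (Protocol 4.1; SAP 2.1) and one participant reclassified.

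- Largest change in a TEAE incidence: 1/6 = 0.167, or 16.7 percentage points.
- Smallest change: 0, if that participant already counts in the same row because of another event.

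**The case against.** The strongest defence is that the sentences can be reconciled through the way a worsening is recorded. With one intensity category per AE, a rise in severity would most naturally appear as a new record with a post-dose onset. The third sentence would then never touch it. This is possible, but neither document says so. Under that practice the first half of the fourth sentence would already count the new record, and the words about worsening would be redundant. What stands is that the conflict depends on the worsening being kept under the same record.

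A second defence reads the third sentence as a specific limit on a general fourth sentence. Case (d) shows that the worsening words would still have some use on that reading. However, the fourth sentence applies to any event and states no such limit. The reading would also count a worsened complaint that began on the morning of dosing and bar one that began the evening before, with no reason given.

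Two stronger readings are tempting, and the documents do not support them.

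- A reader might infer that the first three sentences all exclude the event. Only the third does so expressly. The first says when an event is a TEAE, not that nothing else can be one, and the second says what will be flagged. They fail to capture case (c); they do not forbid it.
- A reader might infer that the end of the window is also wrong, because collection runs "through and including a minimum of 28 calendar days" after the last dose while the second sentence stops short of that day. A TEAE window need not equal the AE collection period. The fourth sentence states no end date, and its silence does not set a second one.

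**Conclusion.** The contradiction is real and is confined to case (c). It lies between the third sentence of the SAP 6.2 TEAE paragraph and the worsening clause of the fourth. As written, the SAP gives no single answer for an AE that starts before the first dose date and worsens after dosing under one record. Programming the third sentence drops an event that the fourth says must count.

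The severity is minor. Only the TEAE classification is affected. All AEs in the active collection period are still recorded on the CRF (Protocol 8.3.1.2), no hypothesis is tested, and the mass balance and metabolite endpoints do not depend on the flag. One reclassified participant changes an incidence by at most 16.7 points.

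This rests on three assumptions: six participants are dosed, worsening is judged against the pre-dose state, and a worsening can stay under its original record. A reader might go further and infer that safety will be under-reported in this trial. That is not supported: the documents give no frequency for such events and do not show which AE tables use the flag.

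**What to change.** Keep the existing window in the second sentence and its provision for onset times where collected. Replace the third and fourth sentences with one rule, for example: *Events that started before dosing are not TEAEs unless they increase in severity after dosing and within the same window, in which case they are flagged as TEAEs.* Align the first sentence with this rule, so that it no longer rests on onset alone. State in the SAP whether the CRF enters a worsening as a new record or under the same record, in agreement with the CRF completion guidance, and program the flag to match.

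The documents do not show which of the two sentences the sponsor intended, so the sponsor should confirm the choice. The wording above keeps post-dose worsening visible. The cost is one SAP paragraph and a change to the flag, with no new data or procedures. The downside is that TEAE counts may be slightly higher than under the third sentence.

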6.3. Other Endpoints

6.3.1. PK Endpoints

Plasma PK Parameters

Blood samples will be collected according to the Schedule of Activities given in the protocol. Plasma samples will be analyzed for concentrations of PF-07265803 and its known circulating metabolites PF-07327859, PF-07327860, PF-07327890 and total radioactivity.

PK parameters will be determined from concentration-time data for plasma. The following parameters will be determined using standard noncompartmental methods:

Table 1. Noncompartmental PK Parameters of Plasma

Parameter	Analysis Scale	Plasma PF-07265803 (and known circulating metabolites PF-07327859, PF-07327860, PF-07327890)	Plasma Radioactivity
AUC _{inf} [*]	ln	D	D
AUC _{last}	ln	D	D
C _{max}	ln	D	D
T _{max}	R	D	D
t _{1/2} [*]	R	D	D
CL/F ^{*,†}	ln	D	D
V _Z /F ^{*,†}	ln	D	D

Key: A=analyzed using statistical model, D=displayed with descriptive statistics,
 ln=natural-log transformed, R=raw (untransformed), *=if data permits, †=where appropriate.

6.3.2. Mass Balance

Mass Balance: cumulative recovery of urinary, fecal, and total excretion of radioactivity over time expressed as percentage of total radioactive dose administered.

6.3.3. Metabolic Profiling and Metabolite Identification

Plasma, urine and fecal samples will be analyzed for metabolites and/or chiral inversion of PF-07265803. Major metabolites and/or stereoisomers of PF-07265803 in plasma, urine, and feces following oral dose of [¹⁴C] PF-07265803 will be identified.

Contributions of each major metabolite to total radioactivity recovered and to circulating radioactivity in plasma will be approximated. Results of the metabolic profiling analysis will be detailed in a separate report and will be summarized within the CSR.

6.3.4. PD Endpoints

None.

6.4. Covariates

None.

7. HANDLING OF MISSING VALUES

For the analysis of safety endpoints, the sponsor data standard rules for imputation will be applied.

7.1. Concentrations Below the Limit of Quantification

In all data presentations (except listings), concentrations below the limit of quantification (BLQ) will be set to zero. (In listings BLQ values will be reported as “<LLQ”, where LLQ will be replaced with the value for the lower limit of quantification).

7.2. Deviations, Missing Concentrations and Anomalous Values

In summary tables and plots of median profiles, statistics will be calculated having set concentrations to missing if 1 of the following cases is true:

1. A concentration has been collected as ND (ie, not done) or NS (ie, no sample).
2. A deviation in sampling time is of sufficient concern or a concentration has been flagged anomalous by the pharmacokineticist.

Note that summary statistics will not be presented at a particular time point if more than 50% of the data are missing.

7.3. Pharmacokinetic Parameters

Actual PK sampling times will be used in the derivation of PK parameters.

If a PK parameter cannot be derived from a subject’s concentration data, the parameter will be coded as NC (ie, not calculated). (Note that NC values will not be generated beyond the day that a subject discontinues).

In summary tables, statistics will be calculated by setting NC values to missing; and statistics will be presented for a particular group with ≥ 3 evaluable measurements.

If an individual subject has a known biased estimate of a PK parameter (due for example to an unexpected event such as vomiting before all the compound is adequately absorbed in the body), this will be footnoted in summary tables and will not be included in the calculation of summary statistics or statistical analyses.

8. STATISTICAL METHODOLOGY AND STATISTICAL ANALYSES

8.1. Statistical Methods

The PK and radioactivity data will be summarized using descriptive statistics.

8.2. Statistical Analyses

8.2.1. Pharmacokinetic Analysis

The PK parameters detailed in [Section 6.3](#) will be listed and summarized for subjects in the appropriate analysis sets (as defined in [Section 5.1.2](#)). Missing values will be handled as detailed in [Section 7](#).

PK parameters will be summarized as specified in the table below. All parameters will be presented in the same table using separate columns for plasma PK, plasma radioactivity.

Table 2. PK Parameters to be Summarized Descriptively

Parameter	Summary Statistics
AUC _{last} , AUC _{inf} , C _{max} , CL/F* and V _Z /F*	N, arithmetic mean, median, cv%, standard deviation, minimum, maximum, geometric mean and geometric cv%.
T _{max}	N, median, minimum, maximum.
t _{1/2}	N, arithmetic mean, median, cv%, standard deviation, minimum, maximum.

- For PF-07265803 only.

Box and whisker plots for individual subject parameters (AUC_{inf}, AUC_{last} and C_{max}) be presented and overlaid with geometric means.

Supporting data from the estimation of t_{1/2} and AUC_{inf} will be listed: terminal phase rate constant (k_{el}); goodness of fit statistic from the log-linear regression (r²); the percent of AUC_{inf} based on extrapolation (AUC_{extrap} %); and the first, last, and number of time points used in the estimation of k_{el}. This data may be included in the clinical study report.

Presentations for PK and total radioactivity (plasma) concentrations will include:

- A listing of all concentrations sorted by subject id and nominal time postdose. The listing of concentrations will include the actual times. Deviations from the nominal time will be given in a separate listing.
- A summary of concentrations by nominal time postdose, where the set of statistics will include n, mean, median, standard deviation, coefficient of variation (cv) and the number of concentrations above the lower limit of quantification.
- A plot of median PK and radioactivity concentrations against nominal time postdose (based on the summary of concentrations by time postdose), where the median concentration-time profiles for plasma PK, and plasma radioactivity will be presented together on the same plot.
- A log-linear plot of the median concentrations against nominal times postdose, as described above.
- Plots of individual concentrations against actual time postdose, where profiles for plasma PK, and plasma radioactivity, will be presented together on the same plot.

- Log-linear plots of individual concentrations against nominal times postdose, as described above.

For summary statistics, median and mean plots by sampling time, the nominal PK sampling time will be used, for individual subject plots by time, the actual PK sampling time will be used.

8.2.2. Mass Balance

Radioactivity excreted in urine and/or feces will be reported as the percentage of the administered radioactivity excreted at each time interval, cumulatively through that interval and the total percent of dose recovered in urine and/or feces.

Percent recovery and cumulative recovery of total radioactivity in urine, feces and emesis (if any) will be determined based on total administered dose.

Individual participant and median data profiles will be graphically presented for the cumulative recovery of radioactivity in urine, feces and their combination. The total recovery of radioactivity in urine, feces and their combination will be listed and summarized using descriptive statistics. Where possible, the rate of excretion of radioactivity will be estimated.

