- c. Procedures to be completed at time of discharge (approximately 144 hours post dose) only, with clinical laboratory tests conducted only after criteria for discharge (footnote "a") are satisfied
- d. Assessments for COVID-19 infection will be done per CRU standards for testing and those described in Section [8.2.5](#)
- e. Starting at enrollment, meals to be served, at clock times matching approximately 0H, 4H, and 9H relative to dosing on Day 1. No meal administered on Day 1 0 h in accordance with the fasted window. To help assure regularity in bowel movements, nutritional composition should contain at least 15 g of fiber per 1000 kcal or fiber capsules containing the equivalent amount of fiber may be administered daily (beginning at least 8 hr after dosing).
- f. Prep D1 Retained Research Samples for Genetics: If not collected on the designated collection day, collect at the next available time point when biospecimens are being collected in conjunction with a participant visit. Sample should be collected prior to dose.
- g. ECG assessment will occur prior to dosing (approximately 1 hour).
- h. Pre-dose vital sign measurements. Predose (approximately 1 hour) vital sign measurements on Day 1.
- i. Safety laboratories consistent with those described in Section [10.2](#)
- j. ECG and vital signs assessment for eligibility may be considered at both screening and Day 1 visit (predose).
- k. Urine drug screen and cotinine conducted at screening and check-in, and urine alcohol conducted at check-in only.

Visit Identifier	Period 1															
Study Day	1						2		3	4	5	6	Early Termination/ Discontinuation			
Hours Before/After Dose	0 ^a	0.5	1	2	3	4	6	9	12	24	36	48	72	96	120	
Study intervention administration	X															
PK blood sampling	X	X	X	X	X	X	X	X	X	X	X	X	X	X	X	
Radioactivity and metabolite ID in blood	X	X	X	X	X	X	X	X	X	X	X	X	X	X	X	
Interval collection for radioactivity and metabolite ID in urine ^b	X	→	→	→	→	→	X	→	X	X	→	X	X	X	X	
Interval collection for radioactivity and metabolite ID in feces ^c	X	→	→	→	→	→	→	→	X	X	→	X	X	X	X	
Emesis Collection for Radioactivity Measurement, if Occurs	X	→	→	→	→	→	→	→	→	X						

- a. Predose sample collection
- b. “Blank” spot urine sample to be collected anytime predose (Day 1) and postdose in intervals of 0-6H, 6-12H, 12-24H, 24-48H, 48-72H, 72-96H, and each subsequent 24H interval up to discharge.

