- c. “Blank” fecal sample to be collected prior to dosing but post admission to CRU and in intervals of each 24H period post dose up to discharge

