2.1. Study Design

This is a Phase 1, open-label, single-period, single-center, non-randomized single oral dose study administering a liquid formulation with 400 mg of PF-07265803 containing 100 μ Ci of [14 C]PF-07265803 to healthy male participants. Participants will be screened for participation in this study within 28 days before dosing on Day 1 to confirm that they meet the inclusion/exclusion criteria specified in protocol Section 5.1.

The duration of this non-randomized Phase 1, open-label, single-center, single-dose study is approximately 7 days, with a 30-day safety follow up. The maximum period of confinement is expected to be 14 days. The minimum period of confinement is expected to be 3 days. Inpatient stay must be extended until >90% radioactive dose administered has been recovered or <1% is excreted in total (urine and feces) in any 24H period for two consecutive days. Maximum confinement will be 14 days.

The expected duration of participation from Screening to the follow-up telephone contact will be approximately 5 weeks (minimum) to 8 weeks (maximum). Approximately 6 participants will be enrolled to study intervention.

On Day-1, participants will be admitted in order to ensure that a group of 6 participants are dosed on Day 1. The study will dose 6 adult male participants in order to ensure that at least 4 participants provide evaluable data. There are no plans to replace participants who are prematurely withdrawn.

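### Does the SAP need a rule for discharged participants in the median cumulative-recovery curve?

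*SAP*

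**What the plan says.** SAP 8.2.2, in the same words as Protocol 9.3.2, asks for recovery per interval, cumulatively and in total, as a percentage of the administered dose. On the plots it states: "Individual participant and median data profiles will be graphically presented for the cumulative recovery of radioactivity in urine, feces and their combination". Total recovery is also listed and summarised. Neither section gives a value for intervals after a participant's discharge.

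Collection ends at discharge. The Schedule of Activities footnotes say, for urine, "each subsequent 24H interval up to discharge" and, for feces, "in intervals of each 24H period post dose up to discharge". Discharge depends on the result: "Inpatient stay must be extended until >90% radioactive dose administered has been recovered or <1% is excreted in total (urine and feces", the second criterion applying to 24-hour periods on two consecutive days, with a 14-day maximum.

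The documents are not consistent on the earliest discharge. SAP 2.1 says "The minimum period of confinement is expected to be 3 days", whereas footnote c of the Schedule of Activities reads "Procedures to be completed at time of discharge (approximately 144 hours post dose) only".

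The only SAP text on missing data in median plots is Section 7.2: "In summary tables and plots of median profiles, statistics will be calculated having set concentrations to missing", in cases where a concentration was not done, had no sample, had a sampling-time deviation of concern or was flagged anomalous. It adds that "summary statistics will not be presented at a particular time point if more than 50% of the data are missing". SAP 8.2.1 invokes Section 7 for the PK parameters; SAP 8.2.2 does not invoke it for recovery.

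**The concern.** Cumulative recovery is a primary endpoint, defined over time, and the median profile is its planned group-level display. Participants leave that profile at times determined by the quantity being plotted. If a programmer applied SAP 7.2 to recovery, each later median would rest only on those still confined. With six participants, a median of three would still be shown, because exactly half missing is not more than half.

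Such a curve can mislead in three ways:

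- It is too low when good recoverers leave by passing 90%.
- It is too high when low recoverers leave because they excrete less than 1% per day.
- It can fall, which no individual's cumulative recovery can do.

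At stake is the late part of one plotted line, and any matching by-interval summary of cumulative recovery, for urine, feces and their combination.

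**Working it through.** The documents give no figure for this point and no excretion rates, so size can only be explored under assumptions.

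**Inputs from the documents.** Six participants. Discharge at more than 90% recovered, or less than 1% in each of two consecutive 24-hour periods. Latest discharge Day 14. A median is suppressed if more than 50% are missing (SAP 7.2, if it applied).

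**Assumptions.** First-order excretion with plateau F and half-life h, so cumulative recovery at time t (hours) is R(t) = F × (1 − 2^(−t/h)). Earliest discharge is 144 h, because the Schedule of Activities marks confinement on Days 1 to 5 without condition, runs blood sampling to 120 h and places discharge procedures at about 144 h.

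**Example 1: the curve falls.** All F = 95%; h = 18, 24, 30, 40, 50, 60 h. The discharge rule gives Days 6, 6, 6, 8, 9, 11.

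| Day | Values of those still collecting (%) | Median, still collecting | Median, last value held |
|---|---|---|---|
| 6 | 94.63, 93.52, 91.59, 87.17, 82.10, 77.00 | 89.4 | 89.4 |
| 7 | 89.83, 85.75, 81.36 | 85.7 | (91.59 + 89.83)/2 = 90.7 |
| 8 | 91.59, 88.37, 84.66 | 88.4 | 91.6 |

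The available-case median drops by 89.38 − 85.75 = 3.6 points from Day 6 to Day 7, where it is 90.71 − 85.75 = 5.0 points below the held median. From Day 9 two or fewer remain, so the 50% rule would suppress the point.

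**Example 2: the curve is too high.** F = 76, 78, 79, 87, 88, 89%; h = 14, 16, 18, 34, 38, 42 h. The three low recoverers leave by Day 7 under the 1% criterion. On Day 10 those remaining have 86.35, 86.90 and 87.30%, median 86.9%. Held forward, the median is (78.88 + 86.35)/2 = 82.6%, a difference of 4.3 points.

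**Example 3: no effect.** h = 14, 18, 22, 30, 40, 50 h; F between 92 and 96%. Four leave at 144 h. Two of six remain, so the 50% rule suppresses every later point, and all plotted points are identical under both approaches.

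**Simulation, combined curve, 144 h minimum** (4,000 six-person trials per setting, lognormal half-lives with CV 30 or 50%). The gap is the largest difference between the two medians at any plotted point, so it overstates the typical displacement.

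| Eventual recovery | Median half-life | Trials in which the curve falls | Mean gap (points) |
|---|---|---|---|
| 95 ± 3% | 20–30 h | 2–38% | 0.04–1.9 |
| 80 ± 6% | 20–30 h | 41–60% | 1.6–2.7 |

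At a 40 h half-life the mean gap is 2.2–3.8 points. For recovery 95 ± 3%, a re-run found no difference at any plotted point in 98% and 92% of trials at 20 h (CV 30% and 50%), and in 54% and 47% at 30 h. With a 3-day minimum stay instead (95 ± 3%, 20–30 h), the curve falls in 17–38% of trials and the mean gap is 1.4–4.0 points.

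**Does the plan lead there?** SAP 7.2 is about concentrations that were not done, not sampled or anomalous. After discharge no collection is scheduled, so no planned sample is missing. SAP 8.2.2 reports recovery cumulatively through each interval, and a sum to which nothing is added keeps its last value. The falling curve needs a rule that the SAP does not state for recovery.

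**Would a carry-forward rule be clearly better?** In Example 1 the held median stops at 91.6%, while the median of all six modelled curves reaches 94.8% on Day 14. It ends 94.8 − 91.6 = 3.2 points low, the same size as the Day 8 gap it removes (91.6 − 88.4 = 3.2). Applied to someone who withdraws early, carrying forward could understate recovery much more.

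**The case for a change.** The strongest case for a change is that the omission concerns a primary endpoint defined over time, and that Protocol 9.3 promised that the SAP would describe how missing data are handled. Staggered exit follows from the discharge rule. An analyst looking for guidance on median plots finds only SAP 7.2, and following it literally gives the distorted line. A 144 h minimum does not remove the problem, as Examples 1 and 2 show. Two or three sentences would settle it, with no new data.

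Much of this stands: the gap is real, the arithmetic is right, and effects are common with slow excretion or lower recovery. Two parts do not carry. First, the distortion needs a rule written for concentrations to be applied to a running sum, which the SAP does not ask for. Second, no single remedy is clearly right. Holding the last value gives a lower bound that can be several points low. Ending the median at the last interval common to all participants, or showing the number contributing with a footnote, deals with the problem as well and imputes nothing.

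**Conclusion.** No change is needed. SAP 8.2.2 leaves out a display detail, and the sensible readings (hold the running sum, or stop the median where participants start to leave) are the ones a competent analyst would choose.

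Under an unfavourable reading, the late median could be displaced by about 4 to 5 points in the constructed examples. Simulated mean largest gaps run from near zero to 3.8 points with a 144 h minimum, and up to 4.0 with a 3-day minimum. These figures rest wholly on assumed excretion rates and recoveries. The inconsistency between the two statements of minimum stay is a separate matter that is not resolved here.

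The consequence is contained. All individual profiles are plotted and each participant's total recovery is listed; neither is affected. The study tests no hypothesis and has no decision rule (SAP 4.1 and 4.2). A cumulative median that fell would be visibly wrong, and a shift without a fall could be checked against the six individual curves.
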